3.0 STUDY DESIGN

- This will be a phase IB, multiple, parallel, and sequential arm, open-label, non-randomized study with no crossover permitted between the arms.

3.1 Study Design Overview (Table 1)

Table 1: Study Schema and Schedule Overview

Indication	Treatment Arm	Treatment	Dosing	Escalation/ de-escalation	Major Endpoints	Fixed N (Apply stopping rules)
Salvage AML	A	OX40 (PF-04518600) alone	D1 and D14 of a 4 wk cycle	4 patients	RP2D/MTD	Closed (as of 6/4/19) 4 treated
	B	Azacitidine + venetoclax + GO	-Aza D1-7 of a 4wk cycle -Ven D1-28 -GO D8		1. CR/CRp/PR per IWG2003	30
	C	Azacitidine + GO + avelumab	-Aza D1-7 of a 4wk cycle -GO D8 -Avelumab D1 and D14		1. CR/CRp/PR per IWG2003	24
	D	Azacitidine + venetoclax + avelumab	-Aza D1-7 of a 4wk cycle -Ven D1-28 Avelumab D1 and D14		1. CR/CRp/PR per IWG2003	24
	E	Azacitidine + avelumab + OX40	-Aza D1-7 of a 4wk cycle -Both OX40 and avelumab D1 and D14		1. CR/CRp/PR per IWG2003	Closed (as of 3/18/20) 0 treated
	F	GO + Glasdegib	Glasdegib po daily in 4 wk cycle -GO D1, D4 and D7		1. CR/CRp/PR per IWG2003	Closed (as of 3/18/20) 5 treated

3.2 Safety evaluation for Arm A (OX40 mAb alone in RR AML):

DLT is defined in section 3.4. A maximum of 4 patients will be enrolled in one dose level.

Only the 0.3 mg/kg dose of OX40 will be evaluated as this was the dose selected to move forward from the solid tumor OX40 single agent dose finding study (B0601002, ClinicalTrials.gov NCT02315066). Up to four patients will be enrolled at the dose level of 0.3mg/kg of OX40. If no more than 1 out of the 4 patients experienced a DLT, then this dose of OX40 will be established as the RP2D for AML and used in the subsequent combinations incorporating OX40 mAb.

3.3 DLT monitoring in each arm (B-F):

Each arm in the study will accrue up to 21 patients (Arms E-F) or up to 24 patients (Arms C-D) and 30 patients (Arm B) with pre-defined toxicity stopping rules to be implemented for early DLT evaluation as per following plan:

Evaluation of the first 6 patients in each treatment arm will occur after all patients have completed two cycles of treatment (or at least 56 days from the first day of treatment). Enrollment will be halted while the first 6 patients in each treatment arm are evaluated for safety. The treatment combination will be considered as safe, and continue to enroll to a total of 21 patients (Arms E-F) or 24 patients (Arms C-D) or 30 patients (Arm B) when there are no more than 1 out of 6 patients with DLTs in the first cycle of treatment. If any patients in the first 6 of each treatment arm withdraw from the study without a DLT event prior to completing the first cycle of treatment, they will be replaced for the assessment of DLT rate. This will allow for early identification of significant toxicities and early stoppage in potentially toxic arms. If 2 or more out of 6 patients have DLTs in the first cycle of treatment in any arm, then an additional 6 patients will enroll at a next lower dose level to be determined by the PI, sponsor (MDACC IND office), and Pfizer team after reviewing the safety, efficacy, and PD data from the first 6 patients enrolled. If no more than 1 out of the additional 6 patients treated with the lower dose level experience DLTs, this treatment combination will be considered as safe and continue to enroll to a total of 21 patients (Arms E-F) or 24 patients (Arms C-D) or 30 patients (Arm B). If 2 or more out of these 6 additional patients experienced DLTs, then this arm will be halted.

The Investigator is responsible for completing the cohort summary template and submitting to the IND office Medical Monitor for review and approval prior to continuing accrual beyond each set of 6 patients in each arm of the study. A copy of the cohort summary should be placed in the Investigator's Regulatory Binder under "sponsor correspondence". This should be submitted after the first six patients.

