Patients were eligible for the azacytidine with nivolumab (AZA+Nivo) trial if they had R/R AML, ECOG ≤ 2 , and adequate organ function. The recommended phase 2 dose was established as azacytidine 75mg/m² Days 1-7 with nivolumab 3mg/kg Day 1 and 14. Courses were repeated approximately every 4-5 weeks indefinitely. 70 R/R AML patients with median age 70 years (range, 22-90), secondary AML (44%), poor risk cytogenetics (34%), median salvage 2 (range, 1-7) were enrolled. The overall response rate was 33% including 15 CR/CRI (22%) (4 CR, 11 CRI), 1 PR, and 7 HI maintained on study >6 months (10%) without ASCT. Additionally, 6 patients (9%) remained on study with stable disease (SD) >6 months. The remaining 41 patients (58%) had no response. 8-week mortality was 10%. Patients who achieved a CR/CRI/PR/HI/SD (n=29; 42%) had significantly improved overall survival (OS) compared with NRs (n=41; 58%) (16.1 versus 4.1 months; $p<0.001$) (Figure 5A). By univariate analysis (UVA) improved ORR was seen in patients with pretherapy BM blast $<20\%$, circulating WBC $</=10,000/\text{mL}$, ASXL1 mutation, and no prior HMA-based therapy. By UVA improved OS was seen in patients who achieved any response or SD (CR/CRI/PR/HI/SD), were salvage 1 status, and had ASXL1 mutation. The med OS with Aza+Nivo compared favorably to historical med OS with azacytidine-based protocols in salvage 1 or 2 patients at MDACC (6.0 versus 4.7 months; $p=0.03$), most prominent improvement seen in salvage 1 patients (11.1 versus 4.1 months; $P<0.001$) (Figure 5B). Grade 3/4 immune related adverse events were observed in 8 (11%) patients, including pneumonitis (n=3), colitis (n=2), and nephritis, skin rash, and hypophysitis (1 each). The majority (12 of 16; 75%) of these occurred in the first 8 weeks after nivolumab initiation. These responded rapidly to steroids.

As of 10/4/18, we have treated a total of 19 patients with relapsed/refractory AML in a phase Ib/II study of the combination of azacitidine and avelumab (NCT02953561). In the phase Ib portion of the study, 6 patients received avelumab at a dose of 3 mg/kg on Days 1 and 14 in combination with azacitidine 75 mg/m² on Days 1-7, followed by 6

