3.4 DLT Definition

DLT is defined as clinically significant non-hematologic adverse event or abnormal laboratory value assessed as unrelated to disease progression, intercurrent illness, or concomitant medications and occurring during the first cycle (28 days) on study that meets any of the following criteria:

- CTCAE Grade 3 AST (SGOT) or ALT (SGPT) for $>/= 7$ days or grade 3 hyperbilirubinemia for $>/= 7$ days

- CTCAE Grade 3 AST (SGOT) or ALT (SGPT) accompanied by grade 2 bilirubin increase
- CTCAE Grade 4 AST (SGOT) or ALT (SGPT) of any duration
- All other clinically significant non-hematological adverse event that is Grade 3 or 4 according to the NCI common terminology criteria version 4.0 with the following exceptions:
 - Grade 3 or 4 nausea, vomiting and diarrhea will be considered DLT only if not controlled by optimal therapy within 72 hours.
 - Grade 3 biochemical abnormalities (e.g., lipase or bilirubin elevation) will only be considered DLT if accompanied by clinical consequences. Grade 3 or 4 electrolyte abnormalities will only be considered DLT if possibly related to study drug and not corrected by optimal replacement therapy within 72 hours.
- Results in discontinuation of therapy
- Any treatment-related death;

Grade 4 neutopenia lasting \geq 42 days from start of cycle in absence of evidence of active AML.

For patients in venetoclax-containing arms (i.e. Arms B and D) who do not receive venetoclax on day 1 due to logistical and/or financial reasons, the DLT period will be extended to 28 days from the first dose of venetoclax. For evaluation of neutropenia-related DLT, the DLT period will be 42 days from the first dose of venetoclax. Evaluation of the first 6 patients in each of the venetoclax containing treatment arms (arms B and D) will occur after all patients have completed two cycles of treatment (or at least 56 days from the first dose of venetoclax). Enrollment will be halted while the first 6 patients in each of these treatment arms are evaluated for safety.

Please see statistics section (section 11.0) for efficacy and toxicity stopping rules to be applied independently to each cohort.

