3.5 Cohort enrollment schema

(A) Arms B-E (Azactidine + venetoclax + GO; azacitidine + avelumab + GO; azacitidine + venetoclax + avelumab; azacitidine + avelumab + PF-04518600)

Arms B-E will commence enrollment in parallel with the OX40 arm (namely Arm A). If multiple are open to enrollment the patient allocation will generally follow a rotating sequence between arms unless the PI (or Co-PI) decide to allot a patient to a particular arm. There will be no separate escalation/dose finding cohorts for

these combination arms, but predefined toxicity stopping rules have been built in to monitor for grade 3/4 drug-related toxicities and to stop or de-escalate dose if >30% grade 3/4 drug-related toxicity is observed in any of the combination arms at any given time as outlined in section 3.3 (DLT monitoring in each arm).

(B) Arm F (GO + Glasdegib)

Arm F is the combination of GO + glasdegib. This arm will commence enrollment in parallel with the OX40 arm (namely Arm A). There will be no separate escalation/dose finding cohorts these combination arms but we have built in predefined toxicity stopping rules to monitor for grade 3/4 drug-related toxicities and to stop or de-escalate dose if >30% grade 3/4 drug-related toxicity is observed in any of the combination arms at any given time as outlined in section 3.0 (DLT monitoring in each arm).

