The treatment combination will be considered as safe and continue to enroll a total of 30 patients (arm B) or 24 patients (arms C-D) or 15 patients (arms E-F) when there are no more than 1 out of 6 patients with DLTs in the first cycle (28 days) of treatment. If any patients in the first 6 of each treatment arm withdraw from the study without a DLT event prior to completing the first cycle of treatment, they will be replaced for the assessment of DLT rate. This will allow for early identification of significant toxicities and early stoppage in potentially toxic arms. If 2 or more out of 6 patients with DLTs in the first cycle of treatment, then additional 6 patients will enroll at a lower dose level. If no more than 1 out of the additional 6 patients treated with lower dose level experienced DLTs, this treatment combination will be considered as safe and continue to enroll to a total of 30 patients (arm B), 24 (arms C-D) or 15 patients (arms E-F). If 2 or more out of these 6 additional patients experienced DLTs, then this arm will be halted.

Arm F will be closed at this time to further enrollment due to lack of clinical efficacy and competing options of higher priority at our institution.

Futility Monitoring for Arms B-F

The primary endpoint of Arm B-F is the achievement of composite complete response (CRc) within 3 months of therapy initiation in patients with RR AML. The method of Thall, Simon and Estey (1995) will be used to monitor efficacy and safety. After the lead-in, shiny applications were used to generate the operating characteristics for toxicity and futility monitoring, respectively (<http://qcprlshinypyro.mdanderson.edu/postprobtoxicity/>, <http://qcprlshinypyro.mdanderson.edu/postprobfutility/>).

The historical data suggested a composite complete response (CRc) rate of 30% in patients with R/R AML with a variety of different therapies^{4,110,119-122}, and a target response rate is 45%. The study arm will be stopped early if the data suggest that:

$$\Pr(P_E > P_H + 0.15 \mid \text{data}) < 0.05,$$

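### The lead-in holds each arm until day 56, but both toxicity rules count essentially first-cycle DLTs only, so treatment-related deaths on days 29-56 usually do not enter the count, and Section 3.5 conflicts with this

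*Combined protocol and SAP*

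**What the plan says.** **Timing of the review.** Section 3.3 states: "Evaluation of the first 6 patients in each treatment arm will occur after all patients have completed two cycles of treatment", with 56 days from the first dose as the alternative, and "Enrollment will be halted while the first 6 patients in each treatment arm are evaluated for safety". Sections 5.2 and 11 repeat the hold. In Arms B and D, Sections 3.4 and 5.2 run the 56 days from the first venetoclax dose.

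**What is counted.** Section 3.3 declares the combination safe "when there are no more than 1 out of 6 patients with DLTs in the first cycle of treatment". Section 11 gives the same rule with the length spelled out: "no more than 1 out of 6 patients with DLTs in the first cycle (28 days) of treatment". With two or more, six further patients enter at a lower dose level.

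**What a DLT is.** The opening sentence of Section 3.4 limits a DLT to an event "occurring during the first cycle (28 days) on study that meets any of the following criteria". Treatment-related death and events that end therapy are listed beneath it. There are two exceptions: grade 4 neutropenia lasting at least 42 days, and, when venetoclax starts late in Arms B or D, a window of 28 days from its first dose (42 for neutropenia).

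**The continuing rule.** Section 11 defines P_T as the probability of DLT, with prior Beta(0.3, 1.7). It stops an arm if Pr(P_T > 0.15 | data) > 0.80, looking at six patients and then every three.

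**Section 3.5.** For the combination arms it describes stopping or de-escalating when more than 30% grade 3/4 drug-related toxicity is seen, without a time limit. For Arms B-E it then sends the reader back to the rule "as outlined in section 3.3 (DLT monitoring in each arm".

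**Approval step.** Sections 3.3 and 5.2 require a summary to go to the IND office for review and approval. Under Section 3.3 the Medical Monitor must approve before accrual continues past the first six.

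**The concern.** The plan pauses each arm for 56 days and then decides on roughly the first 28. A treatment-related death on day 40 is not a DLT under the Section 3.4 wording. That patient has also completed cycle 1, so is not replaced, and stays in the denominator as a patient without a DLT. Because P_T is defined through the same DLT, the continuing rule misses the death too.

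Safety is the first primary objective. A pass opens the arm to 24 - 6 = 18 more patients in Arm C or D, or 30 - 6 = 24 in Arm B. Section 3.5 lets a reader believe that late grade 3/4 toxicity is under a numeric rule, when the section it points to has no such rule.

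**Working it through.** **1. Inputs.** From Section 11: prior Beta(0.3, 1.7), toxicity limit 0.15, stopping threshold 0.80, looks at 6, 9, 12 and so on. From Sections 3.3 and 11: the lead-in passes with at most 1 of 6.

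**2. Reproducing the plan's boundaries.** With x DLTs in n patients the posterior is Beta(0.3 + x, 1.7 + n - x). The boundary is the smallest x with Pr(P_T > 0.15) > 0.80.

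| n | one below the boundary | at the boundary | boundary in the plan |
|---|---|---|---|
| 6 | x = 1: 0.450 | x = 2: 0.801 | 2 |
| 9 | x = 2: 0.642 | x = 3: 0.873 | 3 |
| 12 | x = 3: 0.762 | x = 4: 0.916 | 4 |
| 15 | x = 3: 0.639 | x = 4: 0.839 | 4 |
| 18 | x = 4: 0.745 | x = 5: 0.890 | 5 |
| 21 | x = 4: 0.641 | x = 5: 0.820 | 5 |

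All agree. An exact binomial recursion over the Arm B looks gives early-stopping probabilities of 0.156, 0.345, 0.556, 0.737, 0.864 and 0.976 at true rates 0.10, 0.15, 0.20, 0.25, 0.30 and 0.40. The plan prints 0.163, 0.342, 0.555, 0.731, 0.856 and 0.976. The rule is therefore understood as the plan intends it.

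**3. Two treatment-related deaths on days 29-56 among the first six, with no first-cycle DLT.**

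| | count | lead-in | Pr(P_T > 0.15) |
|---|---|---|---|
| As written | 0/6 | pass | 0.064 |
| Deaths counted | 2/6 | fail | 0.801, above 0.80 |

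This step needs no assumed rate. Three qualifications apply:

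- The score is usually, not always, 0/6. A death falling within 28 days of a late first venetoclax dose would count. So would a patient who already had a qualifying event in cycle 1, or who met the neutropenia item.
- The 0.801 clears the threshold by only 0.001.
- The printed toxicity tables end at 24 (Arm B) and 18 (Arms C-D). These equal 30 - 6 and 24 - 6, so the tables may be meant for patients after the lead-in. On that reading the P_T figures describe the first six of those patients, and the event window is the same.

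**4. What counting would do to the pass probability (illustration only).** Assume a first-cycle DLT rate of 10%, and let c be the rate of counted events on days 29-56 among patients without a first-cycle DLT. The total rate is q = 1 - 0.9(1 - c), and the pass probability is (1 - q)^6 + 6q(1 - q)^5.

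| c | q | pass as written | pass if counted |
|---|---|---|---|
| 0.05 | 0.145 | 0.886 | 0.788 |
| 0.10 | 0.190 | 0.886 | 0.680 |
| 0.20 | 0.280 | 0.886 | 0.464 |
| 0.30 | 0.370 | 0.886 | 0.283 |

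The 10% and every value of c are assumptions. The lower rows are high for treatment-related deaths alone.

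**5. Section 3.5 against Section 3.3.** Two of six patients is 33%, above the 30% in Section 3.5. Read alone, Section 3.5 would act on two drug-related grade 3/4 events in cycle 2. The section it defers to scores them as 0/6. Both cannot be the operating rule.

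**The case against.** **The count does not reopen an arm by itself.** This is the strongest reply, and it stands. Section 3.3 requires Medical Monitor approval after the first six. Section 5.2 repeats review and approval at two cycles and every three evaluable patients after that. Section 9.2 lists the incidence or severity of treatment-related reactions as a ground for terminating. Sections 10.3 and 10.5 require expedited reporting of SAEs. The approver would know of cycle-2 deaths. What is missing is a stated criterion for them, while the written rule calls the arm safe. A reader might infer that an arm with two cycle-2 deaths would simply continue enrolling; the documents do not support that.

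**A first-cycle DLT window is a common choice, and part of the hold has a documented use.** Also true: the neutropenia item and the late-venetoclax window need follow-up past day 28. Neither gives treatment-related deaths in weeks 5-8 a general place in the decision.

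**The background data do not size the problem.** It is tempting to cite Section 2.6.2 on immune events with azacitidine plus nivolumab: "The majority (12 of 16; 75%) of these occurred in the first 8 weeks after nivolumab initiation". That figure pools weeks 1 to 8, so it does not isolate weeks 5-8. Its denominator of 16 exceeds the 8 patients with grade 3/4 immune events, so these events are not shown to be DLT-type. The drug is not avelumab, and Arm B contains no PD-L1 antibody. In the azacitidine plus avelumab study, Section 2.6.2 reports no DLTs in phase Ib and no deaths considered related. One might also assume that 30-40% of patients have a DLT-type event by day 56, which would make the loss look very large. No such rate appears in the documents.

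**Conclusion.** The concern holds in a limited form. By the written rules, the lead-in count and the P_T rule ignore treatment-related deaths on days 29-56 except in the cases listed in the working, although enrolment is held so that those days can be observed. Two such deaths move the score from 2/6 to 0/6, and Pr(P_T > 0.15) from 0.801 to 0.064. Sections 3.3 and 3.5 also contradict each other on the window and must be reconciled.

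The conclusion rests on reading the 28-day limit in the opening of Section 3.4 as governing every item below it, which the wording requires. How often an arm would be wrongly passed cannot be estimated, because the documents give no cycle-2 rate. Nor do they show that every DLT criterion ought to run to 56 days; that is a design choice on which informed statisticians can differ. The change is worth making before the lead-in decisions because a human approval step without a criterion is a weaker protection than the plan appears to offer.

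**What to change.** 1. Reconcile Sections 3.3, 3.4, 3.5 and 11 so that all state the same event window, including what the time-unlimited wording in Section 3.5 means.
2. Count a treatment-related death observed by the day-56 review as an event in both the lead-in count and the P_T rule, so that the two rules cannot disagree about the same patients. For patients enrolled after the lead-in, apply the same day-56 limit to each patient and enter the death at the next look. Keep the Arm B and D anchor at the first venetoclax dose.
3. In the cohort summary sent for approval, report day 29-56 DLT-type events beside the 28-day count.
4. State whether the P_T tables include the six lead-in patients.

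**Cost.** Text changes in four sections and one added line in the summary. The 56-day hold already exists, and survival status is already needed because 8-week mortality is a secondary endpoint. The boundaries depend only on the prior, the 0.15 limit, the 0.80 threshold and the counts, so they do not move. The team should confirm that 15% remains the intended limit once late deaths are included. The downside is that an arm with late treatment-related deaths is less likely to pass; in the illustration, 0.886 becomes 0.788 at an assumed 5% rate.

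Whether the other DLT criteria also move to 56 days is for the sponsor to decide. If they do, the replacement rule, which now covers only withdrawal before the end of cycle 1, and the toxicity operating characteristics must be redone.

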5.3 TREATMENT CYCLES

- One cycle of therapy is defined as 28 days (+/- 4 days). Patients will receive one cycle of therapy every 28 days (+/- 4 days).
- Cycles may be started early (but not earlier than day 24) for patients with active disease if judged in the best interest of the patient.
For the dose finding PF-04518600 monotherapy cohort, the DLT defining period is 28 days. As such, cycle 2 should not be commenced before 28 days for the patients being treated in the lead-in cohort.
- Subsequent cycles may be delayed for recovery of toxicity or other medical conditions (e.g. infections). Delays in the start of subsequent cycles greater than 8 weeks will be acceptable only for patients who are deriving clinical benefit and after discussion with the principal investigator of potential risk/benefit ratio and clear documentation in the medical record of the reason for continuation and perceived benefit to the patient from continuation of this therapy.
- In instances where one drug has to be discontinued transiently because of safety, the administration of the other drug/s may continue as scheduled.
- Therapy will be held during phase II of the study, for grade 4 neutropenia or grade 4 thrombocytopenia lasting \geq 42 days from the start of each cycle, in the absence of any evidence of active AML in the bone marrow or peripheral blood. Delays in start of subsequent cycles greater than 42 days will be acceptable only for patients who are deriving clinical benefit and after discussion with the principal investigator of potential risk/benefit ratio.
- If the peripheral counts do not recover (ANC $<0.5 \times 10^9/L$ and/or platelets $<25 \times 10^9/L$) but there is evidence of residual leukemia by morphology or flow-cytometry in the bone marrow, subsequent cycles can be administered at the discretion of the treating physician not earlier than 24 days after the prior cycle in

the phase II portion of the study.

- For patients who discontinue therapy, the reason for treatment discontinuation will be captured.

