11.0 STATISTICAL CONSIDERATIONS

This is an open-label Phase IB/II multi-arm study. The primary objectives are to determine the maximum tolerable dose (MTD) and identify the dose of PF-04518600 (Arm A), and to evaluate the composite complete response (CRc) within 3 months of therapy initiation of the combination therapies: Azacitidine + venetoclax + GO (arm B), Azacitidine + avelumab + GO (arm C), Azacitidine + venetoclax + avelumab (arm D), Azacitidine + avelumab + PF-04518600 (arm E), and GO + glasdegib (arm F), in patients with relapsed/refractory AML. A total of up to 87 patients will be enrolled in the study (arms with up to 24 patients per arm in arms C-D and 30 patients in arm B, in addition to the 4 patients enrolled in arm A and 5 patients enrolled in arm F at the time of closing these two arms).

Dose safety evaluation for Arm A (PF-04518600 alone in RR AML):

The 0.3 mg/kg dose of PF-04518600 will be evaluated as this was the dose selected to move forward from the solid tumor PF-04518600 single agent dose finding study (B0601002, ClinicalTrials.gov NCT02315066). Up to four patients will be enrolled at the dose level of 0.3mg/kg of PF-04518600. This arm will be closed at this time to further enrollment due to lack of clinical efficacy and competing options of higher priority at our institution.

Lead-in safety evaluation for Arm B-F

A lead-in safety evaluation for Arm B-F will be conducted to confirm the safety and tolerability of the treatment combination. Up to 30 patients in arm B, 24 patients in arms C-D and up to 21 patients in arms E-F will be enrolled. Enrollment must be halted while the first 6 patients in each treatment arm are evaluated for safety (i.e. after all patients have received 2 cycles of therapy, or been followed for at least 56 days from the start of treatment).

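### For late venetoclax starters in Arms B and D, the lead-in counts DLTs and replaces patients by first cycle, although Section 3.4 runs their DLT period past it

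*Combined protocol and SAP*

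**What the plan says.** - **Decision rule.** Section 3.3 clears an arm when there are "no more than 1 out of 6 patients with DLTs in the first cycle of treatment". Section 11 has the same rule with the length added: "no more than 1 out of 6 patients with DLTs in the first cycle (28 days) of treatment".
- **Replacement.** In both sections, a lead-in patient is replaced only on leaving before the end of cycle 1 ("withdraw from the study without a DLT event prior to completing the first cycle of treatment, they will be replaced").
- **DLT period.** Section 3.4 starts from events "occurring during the first cycle (28 days) on study". For patients in Arms B and D who miss day-1 venetoclax for logistical or financial reasons, "the DLT period will be extended to 28 days from the first dose of venetoclax". For neutropenia, "the DLT period will be 42 days from the first dose of venetoclax".
- **Review clock.** Sections 3.4 and 5.2 hold enrollment in Arms B and D until the six have completed two cycles or reached 56 days from first venetoclax. Section 3.3 counts the 56 days from the first day of treatment. Section 11 requires that patients have "been followed for at least 56 days from the start of treatment".
- **Late starts.** The Arm B and Arm D schedules in Section 5.2 foresee delayed venetoclax, set no limit on the delay, and do not treat it as a deviation.
- **Early cycles.** Section 5.3 says "Cycles may be started early (but not earlier than day 24) for patients with active disease". It then bars cycle 2 before 28 days for a lead-in cohort, directly after a sentence about PF-04518600 monotherapy.

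**The concern.** The six-patient decision opens Arm B to 30 patients and Arm D to 24. It should rest on six patients observed for the whole period in which an event would be a DLT. For a late venetoclax starter, that period ends after cycle 1. Applied as written, the rules in 3.3 and 11 can include a patient whose period was never completed. They also leave out an event that 3.4 calls a DLT. Both errors run towards clearing the arm.

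No other text closes the gap. The rule that patients not evaluable for DLT are replaced appears only under Arm A in Section 5.2. That section refers to evaluable subjects for Arms B to F without defining DLT evaluability. Section 5.4.8 makes anyone who received one dose of any drug in the combination evaluable for toxicity.

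**Working it through.** **1. The plan's own figures.** The documents give no clearance probability for the 1-of-6 rule, but they do tabulate the continuing toxicity rule. With the stated Beta(0.3, 1.7) prior and stopping when Pr(P_T > 0.15 | data) > 0.80, the boundaries reproduce exactly: 2/6, 3/9, 4/12, 4/15, and for Arm B also 5/18 and 5/21. At a true rate of 0.30, an exact recursion gives a stopping probability of 0.864 for Arm B (table: 0.856) and 0.781 for Arms C-D (table: 0.771).

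**2. The windows.** If venetoclax starts on study day d, the 28-day period ends on day d + 27 and the 42-day neutropenia period on day d + 41.

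| Venetoclax start | 28-day period ends | 42-day period ends | 56 days from first venetoclax |
|---|---|---|---|
| day 1 | 28 | 42 | 56 |
| day 8 | 35 | 49 | 63 |
| day 15 | 42 | 56 | 70 |
| day 16 | 43 | 57 | 71 |
| day 29 | 56 | 70 | 84 |

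Any start after day 1 takes the 28-day period past day 28. For patients still under observation, a review on day 56 (two 28-day cycles, or 56 days from start of treatment) covers the 28-day period if d ≤ 29, but the 42-day period only if d ≤ 15. A review at 56 days from first venetoclax covers both for any d.

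**3. A worked patient.** Azacitidine starts on day 1 and venetoclax on day 15. The patient withdraws consent on day 32 without a DLT. The 3.4 period runs to day 42 (day 56 for neutropenia). Cycle 1 was completed on day 28, so 3.3 and 11 do not replace the patient, who counts as DLT-free. If the patient had stayed and had a qualifying event on day 35, it would be a DLT under 3.4 but outside the first-cycle count.

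**4. Illustrative effect on clearance.** With six full windows and DLT risk p, P(clear) = (1−p)^6 + 6p(1−p)^5. This is 0.420 at p = 0.30 and 0.233 at p = 0.40.

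Assume that two of six start venetoclax on day 15 and are counted only to day 28, which is 14/28 = half of the period. Assume also a constant hazard. Each of the two then has observed risk q = 1 − (1−0.30)^0.5 = 0.163.

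- P(0 DLTs) = 0.70^4 × 0.837^2 = 0.168
- P(1 DLT) = 4 × 0.30 × 0.70^3 × 0.837^2 + 2 × 0.163 × 0.837 × 0.70^4 = 0.288 + 0.066 = 0.354
- P(clear) = 0.522

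With three such patients it is 0.577. At p = 0.40, the figures for two and three are 0.330 and 0.389.

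The hazard shape matters. If a fixed share of each affected patient's risk is seen instead, two patients at p = 0.30 give 0.475 (three quarters seen), 0.532 (half seen) or 0.652 (none seen).

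**5. After continuing monitoring.** I carried the two-patient constant-hazard case through the tabulated boundaries. Later patients were fully observed, and 2/6 was treated as a stop (the plan first tries a lower dose).

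| True risk | Arm B P(stop), full → two half windows | Arm D P(stop), full → two half windows |
|---|---|---|
| 0.30 | 0.864 → 0.826 | 0.781 → 0.722 |
| 0.40 | 0.976 → 0.965 | 0.937 → 0.908 |

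**The case against.** **Section 3.4 governs.** It defines the DLT, extends the period expressly, and repeats the six-patient hold for Arms B and D. Many teams would count a day-35 event. That is a sensible reading. However, Section 11 states the decision rule with its own 28 days and no exception, and 3.4 never mentions replacement.

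**Patients who stop treatment remain under observation.** This stands, and it narrows the point. Section 9.1.4 follows them for toxicity for at least 100 days after last treatment. The notes to Table 13 say at least 30 days, and Section 10.1 records adverse events to 30 days after the last dose. A reader might infer that a patient who comes off treatment for progression on day 32 has an unobserved window. The documents do not support that. For such a patient the question is mainly which events count. Observation is lost only through withdrawal of consent, loss to follow-up or death.

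**Early cycle 2.** A reader might also infer that 5.3 lets lead-in patients in Arms B to D start cycle 2 on day 24 and so cuts their DLT period short. The documents do not establish this. The 28-day bar names a lead-in cohort, and Sections 5.2 and 11 use lead-in for Arms B to F. Because the bar follows a sentence on PF-04518600 monotherapy, its scope is unclear. The 3.4 period also runs in calendar days, so an early cycle 2 would not shorten it.

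**The figures are assumed.** This stands. The documents give neither the number of late starters nor the timing of risk. The illustration also gives days 1 to 14 no DLT risk, although other drugs in the combination are being given then. Clearance is not final either, because toxicity is monitored every three patients. A DLT missed in the lead-in does, however, remain missing from those cumulative counts.

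**Conclusion.** The mismatch holds on the text, for late venetoclax starters in Arms B and D. The decision count and the replacement rule use the first cycle, while the DLT definition uses a later period. The 56-day clock has two starting points. A patient lost to observation after cycle 1 can be kept as DLT-free, and a DLT in the extended period can fall outside the count. The scope of the 28-day sentence in 5.3 is an ambiguity to resolve, not an established gap.

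Only the direction is firm: incomplete windows can only raise the chance of clearance. As an illustration at a 30% risk, with two of six windows half observed under a constant hazard, clearance rises from 0.42 to about 0.52. After continuing monitoring, the probability of stopping falls by about 4 points in Arm B and 6 in Arm D. At a 40% risk, the falls are about 1 and 3 points. With no late starters, this effect is zero. The plan should still be corrected, because the rule decides whether a triplet is expanded and the correction is cheap.

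**What to change.** 1. In Sections 3.3 and 11, count DLTs in the DLT period defined in Section 3.4, by calendar day whatever cycle the patient is in.
2. In the same places, replace any lead-in patient who leaves observation without a DLT before completing that period. State whether the 28-day or the 42-day neutropenia window governs replacement. The neutropenia criterion outlasts a 28-day cycle in every arm, so the choice affects how many patients are replaced.
3. Use the anchor in 3.4 and 5.2 (first venetoclax dose in Arms B and D) for the 56 days in both 3.3 and 11.
4. Reconcile the day-24 and 28-day sentences in 5.3 by stating which cohorts each covers.

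The cost is wording, an occasional extra replacement patient, and a slightly longer lead-in hold when venetoclax supply is late. Replacements would be more frequent if the 42-day window is chosen.
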